4.1 Selection of Study population

Aim 1A. No individual HCW or patient participants will be enrolled in this study. In this cluster-randomized trial, hospital units will be selected for participation and randomized to either the intervention (direct gloving) or usual care strategies. Potential units for participation will include Adult ICU, General Pediatrics, Adult Emergency Department and Inpatient Hemodialysis Units at

the four participating hospitals (University of Maryland Medical Center, RA Cowley Shock Trauma Hospital, University of Iowa Hospitals and The Johns Hopkins Hospital). As outlined above, among the 43 possible units meeting this description, units will be selected for participation based on the results of baseline hand hygiene and glove compliance. 14 total units will be selected for study inclusion and will be randomized to either intervention or usual care. In each case, hospital leadership, unit leadership and the department of infection prevention will assent to unit participation. HCWs in each unit will be observed regarding compliance with hand hygiene and glove use; this data will be collected in aggregate for each unit and no individual healthcare worker data will be collected. This data is currently being collected at each facility as part of standard infection prevention practice.

Aim 1B. Individual HCWs from the above participating units will be randomly selected for participation. Individuals who consent will have samples taken of gloved hands after donning as outlined above.

4.2 Inclusion Criteria

Aim 1B:

- Adults > 18 years
- HCWs at one of the study sites
- HCW donned non-sterile gloves upon entry to a Contact Precaution-patient room

4.3 Exclusion Criteria

- Informed Consent not obtained
- Food services employee
- Environmental services (housekeeping) employee

4.4 Participant Withdrawal

Participants will be unable to withdraw from the study since any data or samples collected will be de-identified. Those who do not wish to participate with sampling of gloves will be able to do so without repercussions for declining participation.

5 Informed Consent Process

5.1 Recruitment

Aim 1A. Ward/units will be recruited for participation in this study. This study aims to recruit from the following unit types at the UMMC: Adult ICUs, General Pediatric Wards, Emergency Departments (ED, TRU) and Inpatient Hemodialysis units. Consideration for a unit/wards participation in this study will be reviewed with the UMMC Department of Infection Prevention and Hospital Epidemiology. In addition, decisions for participation will be made in concert with Infection Prevention AND the individual unit leadership (e.g. Medical and Nursing directors). In the baseline period (previously described), compliance with HH and gown/glove use will be collected and units with similar rates of compliance (across all three sites, U Maryland, Iowa and Hopkins) will be included as study participants and will be randomized to receive the intervention or usual care. Interactions with the participating units will include education and data collection regarding compliance with infection prevention practices.

Aim 1B. The investigators will station themselves outside the rooms of patients on Contact Precautions within the units participating in the study; these rooms will be identified by the hospital infection control signs outside the door. As HCWs approach the room with intent to enter; the investigators will introduce themselves, briefly describe the study, study procedures, and will ask HCWs if they would consent to participate. It will be made clear that participation is voluntary and that there are no repercussions for declining participation. The investigators will give verbal information about the study and have written information also available. HCWs will have gloves sampled by direct sampling by agar plate.

5.2 Alteration of Consent

Aim 1A:

We have requested an exemption of consent since no individuals (i.e. no human subjects) are being enrolled in the study and data collection is occurring at the aggregate (unit) level - we are not collecting data regarding individual patients or HCWs.

Aim 1B:

We are requesting a waiver of written documentation of informed consent for participants in this study. HCWs will be approached regarding participation upon entry to patient rooms. Trained research staff will verbally describe the study procedures, requirements, benefits and risks to the subject. The subject will have ample time to ask questions and consider if they want to participate in the study. The subject will provide verbal consent before any procedures are done specifically for the study. The subject may withdraw consent at any point in the study. We are requesting a waiver of written documentation of informed consent - as this might result in greater risk to the participant because it would require that we collect identifying information that we otherwise do not need.

5.3 Waiver of HIPAA Authorization

We are not collecting PHI.

5.4 Informed Consent Process

Aim 1A:

We have requested an exemption of consent since no individuals (i.e. no human subjects) are being enrolled in the study and data collection is occurring at the aggregate (unit) level - we are not collecting data regarding individual patients or HCWs.

Aim 1B:

This minimal risk study involves direct observation of HH and in randomly selected interactions culturing of gloves by direct imprint on agar plates. It is not scientifically necessary for the study to collect any identifying information about the HCW. By obtaining written informed consent we would need to collect identifiers from participants and thus would place participants at greater than needed risk based on confidentiality. A waiver of written documentation of informed consent has been recommended previously from the IRB on prior similar protocols (ie- culturing skin or attire of HCWs)

6 Statistical Plan

6.1 Analysis Plan

Aim 1A:

We will assess whether primary and secondary outcomes are significantly different in the experimental and usual care groups using the generalized estimating equations (GEE) approach with an unstructured working correlation matrix to adjust for clustering. We will perform multivariate analyses using GEE adjusting for covariates such as baseline compliance with HH and frequency of Contact Precautions. Analyses will be conducted at the level of the participating unit and will follow the intention to treat approach.

Aim 1B:

The primary analysis will be an intention-to-treat analysis where the gloved hands of HCWs sampled in the usual care group will be compared to those in the Intervention group regardless of HH activity. A secondary, as-treated analysis will be performed where HCWs who were observed to perform HH and then don gloves will be compared to those in which gloves were directly applied without performing HH. The primary, intention-to-treat analysis will provide great insight into the effectiveness of this intervention while the secondary, as-treated analysis will validate efficacy.

The primary outcome, total bacterial colony forming units (CFUs) > 30 of gloved hands, will be compared between the two groups using a comparison of proportions. In this case a one-sided $p < 0.025$ will be statistically significant for noninferiority. We will also compute a two-sided 95% confidence interval for the relative risk of CFUs > 30 comparing direct gloving to HH + gloving, where the upper bound of the confidence interval < delta will be considered statistically significant. In this analysis, we define the non-inferiority margin, or delta, equal to 1.15. We feel (in consultation with microbiologists and HH experts) that if glove reuse (intervention) were found non-inferior to usual care by a 1.15 margin (i.e. a difference of 15%) that this would be enough to lead to change in practice. Robust empirical standard errors will be calculated using generalized estimating equations with an independence working correlation matrix to account for within-site clustering for sample proportions. A secondary analysis will compare groups using CFUs as a count outcome. We will compute a two-sided 95% confidence interval for the relative mean of CFUs on gloved hands comparing the intervention to the usual care group. The upper bound of the confidence interval < delta will be considered statistically significant, where delta is 1.15. The secondary outcomes, presence of pathogenic bacteria and total number of pathogenic and non-pathogenic bacteria present, will be analyzed like the primary outcome.

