1.5 Risk Benefit Ratio

The potential benefits of this study outweigh the minimal risks to participants.

2 Study Objectives, Aims and Hypothesis

Aim 1A: Perform a multicenter, cluster randomized trial to evaluate the efficacy of a direct gloving strategy to improve compliance with infection prevention practices (i.e. HH and glove use).

Hypothesis: When compared to the standard practice of performing HH and then donning gloves, directly gloving when gloves are indicated will increase compliance with HH and glove use.

Aim 1B: Perform a nested multicenter validation study, where gloved hands of HCWs will be randomly sampled to determine bacterial contamination of non-sterile gloves after donning.

Hypothesis: When compared to the standard practice directly gloving when gloves are indicated will have no effect on bacterial contamination of gloves.

3 Study Design and Procedure

Aim 1A:

Study Design: We will perform a cluster-randomized trial to include 14 patient care areas (i.e. units) at the University of Maryland Medical Center (UMMC), the R Adams Cowley Shock Trauma Center (STC), University of Iowa Hospitals (UIH), and Johns Hopkins Hospital (JHH). Each unit will be randomly assigned to the intervention or usual care group. Randomization will be stratified by unit type: adult intensive care, general pediatric wards, emergency departments and inpatient hemodialysis units. One unit from each of the four types at UMMC, UIH, and JHH will be selected for study participation and will be randomized; and two units (one Adult ICU and the Trauma Resuscitation Unit (comparable to the Adult ED)) will be selected and randomized from Shock Trauma. We have specifically chosen these diverse areas to avoid any potential crossover of effect from one study unit to another as units have very different personnel with very little crossover of care.

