In order to account for differences in baseline compliance with infection control practices including HH and glove use, baseline rates of compliance will be observed across all available units (this includes 4 adult ICUs, 3 general pediatric wards units, 1 ED and 1 inpatient HD unit at UMMC and 4 adult ICUs and 1 ED at Shock Trauma). In the study period prior to randomization; the final units will be selected based on similar baseline compliance. For example, there are 11 general pediatric wards across three sites. Baseline data will be collected and compared across all 11 wards. One pediatric unit from each facility with the closest baseline composite HH and glove compliance rates will be selected. Thus we are matching 3 general pediatric wards (one from each site) based on pre-intervention outcomes of interest to improve power and minimize the impact of measured and unmeasured confounders. Once selected, the units will be randomized to the intervention or usual care group. This process will be done for each unit type (e.g. adult ICU).

The study will begin with a 6-month period of baseline data collection in which HH and infection prevention compliance will be recorded in all units that are potentially available for inclusion as described above. During that time period the investigative team will develop and refine educational, training and data collection tools. Following this baseline period, a short “wash-in” period of 3 months will be used to educate and train HCWs in the participating units regarding expected infection prevention practices of HH and glove use. The intervention period will be a full 12 months. This will allow the intervention to be tested over a full calendar year accounting for differences in seasonality as well as different levels of training across an academic year.

All participating units regardless of intervention status will receive education regarding policies and procedures for compliance with infection prevention strategies including HH and glove/gown use. This education will be identical in both groups (intervention and usual care) and will be consistent with published guidelines (WHO/CDC) with the exception of HH prior to donning non-sterile gloves - which according to existing guidelines is an uncertain area where research is needed. HCWs from units randomized to the usual care group will receive education that states that they should perform HH prior to donning non-sterile gloves. HCWs from units randomized to the

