intervention group will receive education that states that HH is not necessary prior to unsterile glove use. Both units will receive education around other necessary moments for HH and as stated this education will be identical for both groups.

Data collection in both the baseline and intervention phases will be as follows:

Primary Outcome:

Composite Compliance with expected infection prevention practices upon entry to Contact Precaution-patient rooms. HCWs in the usual care group will be recorded as compliant if HH AND glove use is observed at room entry; HCWs in the intervention group only need to have glove use observed to be considered compliant.

Secondary Outcomes:

1. Compliance with glove use upon entry to Contact Precaution-patient rooms for both groups
2. Compliance with HH upon entry to ALL patient rooms
3. Compliance with HH upon exit to ALL patient rooms

Additional Information collected will include: date, time and location (i.e. hospital/unit) of observation and the role of the HCW observed (e.g. MD, RN, other).

Note that all data collected is completely anonymous and no HCW identifying information will be collected nor reported

Aim 1B:

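### The Aim 1A adjusted model does not name the unit's own baseline of the analysed outcome; using it as a single covariate would sharpen the estimates, chiefly for glove use, at the cost of wording.

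*Combined protocol and SAP*

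**What the plan says.** Section 6.1 (Aim 1A) describes two analyses. The first compares the groups by a "generalized estimating equations (GEE) approach with an unstructured working correlation matrix to adjust for clustering", with no covariate or stratum term. The second is multivariable, "adjusting for covariates such as baseline compliance with HH and frequency of Contact Precautions". The section does not say which is primary. It adds: "Analyses will be conducted at the level of the participating unit and will follow the intention to treat approach".

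Section 3 (Aim 1A) describes a design with more baseline information than that list uses:
- **Stratification:** "Randomization will be stratified by unit type: adult intensive care, general pediatric wards, emergency departments and inpatient hemodialysis units".
- **Baseline period:** a "6-month period of baseline data collection in which HH and infection prevention compliance will be recorded", covering all candidate units.
- **Same measurements in both phases:** "Data collection in both the baseline and intervention phases will be as follows". The list that follows contains the composite primary outcome, glove use, HH at entry and HH at exit.
- **Matching:** units are chosen within type for similar baseline composite compliance. The paediatric example says "we are matching 3 general pediatric wards (one from each site) based on pre-intervention outcomes of interest to improve power".

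Section 3 defines primary-outcome compliance as HH plus gloves in the usual care arm and gloves alone in the intervention arm.

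**The concern.** By the time of randomisation every unit has a six-month baseline rate for each Aim 1A outcome, and its type is a design factor. Section 6.1 carries neither into the model by name, except for HH.

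The fit of baseline HH varies by outcome. It is in effect the right baseline for the two HH secondary outcomes. It is one component of the usual care composite. It is not a component of glove use, which is secondary outcome 1 and is all that counts for the primary outcome in the intervention arm.

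With 14 randomised units, differences between units can dominate the standard error. A unit's earlier rate of the same outcome is a natural predictor of its later rate. Leaving it out keeps predictable variance in the error term and leaves any chance imbalance in baseline glove use between the arms uncorrected.

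**Working it through.** **Inputs from Section 6.2:** 14 units; 500 observations per unit; alpha 0.05; ICC 0.001 or 0.01; primary outcome about 40% with an effect of about 30 points; glove use 70-80% with an effect of about 10 points.

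**Assumptions, not in the documents:** 7 v 7 allocation; two-sided alpha; a t reference on between-unit degrees of freedom (df); and rho, the correlation between a unit's baseline rate and its underlying follow-up rate, taken as 0.3, 0.5 or 0.7.

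**1. The plan's own power figures.** Normal approximation, effective n per arm = k × 500 / [1 + 499 × ICC], with k units per arm.
- Primary, 40% v 70%, 2 v 2 units: design effect 1.499 at ICC 0.001 and 5.99 at ICC 0.01. Power exceeds 99.9% at both (plan: above 90%).
- Glove use, 70% v 80%, 2 v 2 units, ICC 0.001: 98.9% (plan: above 90%).
- Glove use, 4 v 4 units, ICC 0.01: about 85% (plan: above 85%).

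The plan's figures reproduce by this method.

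**2. Share of variance that a unit-level covariate can reach.** The variance of a unit's mean is proportional to ICC + (1 − ICC)/500.
- ICC 0.01: 0.01/0.01198 = 83% is between units.
- ICC 0.001: 0.001/0.002998 = 33% is between units.

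**3. Effect of adjustment, glove use 70% v 80%.**

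Var(difference) = [0.7×0.3 + 0.8×0.2]/7 × [ICC(1 − rho²) + (1 − ICC)/500] = 0.05286 × [...]

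The half-width is t × SE, with 12 df unadjusted (t = 2.179), 11 df with one covariate (2.201) and 8 df with baseline plus unit type (2.306). Power is from the noncentral t.

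At ICC 0.01:
- Unadjusted: SE = √(0.05286 × 0.01198) = 0.0252
- rho 0.5: √(0.05286 × 0.00948) = 0.0224
- rho 0.7: √(0.05286 × 0.00708) = 0.0193

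| ICC | Model | Half-width, points | Power |
|---|---|---|---|
| 0.01 | unadjusted | 5.48 | 95% |
| 0.01 | own baseline, rho 0.3 / 0.5 / 0.7 | 5.33 / 4.93 / 4.26 | 96 / 98 / >99% |
| 0.01 | plus unit type (4 df), rho 0.3 / 0.5 / 0.7 | 5.58 / 5.16 / 4.46 | 95 / 97 / 99% |
| 0.001 | unadjusted | 2.74 | ~100% |
| 0.001 | own baseline, rho 0.5 / 0.7 | 2.65 / 2.53 | ~100% |
| 0.001 | plus unit type (4 df), rho 0.5 / 0.7 | 2.78 / 2.66 | ~100% |

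In the rows with unit type, rho is the joint correlation of baseline and type with the follow-up rate.

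The one-covariate formula applies to any single baseline. If baseline HH had rho 0.3 with glove use and baseline glove use had rho 0.5, naming the former would give 5.33 points where 4.93 was available.

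**4. Break-even for the 4-df model.** It narrows the interval only if baseline and type together explain more than 13% of between-unit variance at ICC 0.01, or 32% at ICC 0.001.

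**5. Primary outcome, 40% v 70%, ICC 0.01.** The unadjusted SE is √([0.24 + 0.21]/7 × 0.01198) = 0.0278, so the effect is about 0.30/0.0278 = 10.8 standard errors. Power is about 100% with or without adjustment. The half-width falls from 6.0 points to 5.4 (rho 0.5) or 4.7 (rho 0.7).

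**6. If the ICC were above the plan's range (assumed values).** Glove power rises from 61% to 72% or 85% at ICC 0.03, and from 42% to 52% or 67% at ICC 0.05 (own baseline alone, rho 0.5 or 0.7).

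**The case against.** The strongest replies are these.

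- **The list is open.** The covariates are given as examples, so own-outcome baselines and unit type are not excluded. This stands. A reader might infer that the plan has chosen the wrong baseline or ruled out the right one; the text does not support that. But an open list with no primary model named leaves the covariates to be chosen after results are seen, and the better choice is already available.
- **Baseline HH is often a sound choice.** This stands for HH at entry and exit, and in part for the composite. On the plan's figures (HH 40-50%, gloves 70-80%, composite about 40%), HH is the limiting component. The objection leaves glove use and the intervention arm's primary outcome untouched.
- **The matching is not wasted.** A reader might infer that the design's matching goes unused. It does not: choosing units with close baseline composites restricts baseline spread whatever model is fitted. It may also lower rho for that covariate.
- **The baseline composite is itself an imperfect match for the primary outcome.** In the intervention arm the follow-up measure is gloves alone. This stands as a limit on the gain, though the composite does include glove use.
- **The trial is not short of power.** This stands for the primary outcome, and for glove use at ICC 0.001. The large gains in step 6 need ICCs three to five times the plan's upper value.
- **Degrees of freedom are scarce.** Adding unit type can widen the interval: 2.74 to 2.78 points at ICC 0.001 with rho 0.5, and 5.48 to 5.58 at ICC 0.01 with rho 0.3. This is why the single-covariate model should lead.

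**Conclusion.** The concern holds as a worthwhile, inexpensive improvement to the Aim 1A analysis. It is not an error that threatens the primary conclusion. Section 6.1 should name each outcome's own baseline. The single-covariate model narrowed the interval in every case tried here, whereas adding unit type did not.

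The gain is material for glove use at ICC 0.01: about 10% off the interval width at rho 0.5 and 22% at rho 0.7. At ICC 0.001 it is about 3% and 8%. For the primary outcome the benefit is precision and protection against chance imbalance, not power.

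The sizes rest on assumed values of rho, on 7 v 7 allocation and on two-sided testing. They are measured against the unadjusted comparison; against a model already containing baseline HH the gain would be smaller wherever HH predicts the outcome. The documents give no baseline-to-follow-up correlation, so the actual gain cannot be fixed in advance.

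**What to change.** In Section 6.1, Aim 1A:

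1. Define the main model as treatment plus the unit's own six-month baseline rate of the analysed outcome: composite for the primary outcome, glove use for secondary 1, entry HH for secondary 2, exit HH for secondary 3.
2. State that this model is primary and that its covariate set is closed.
3. Report the unadjusted comparison as supportive.
4. Report a model that adds unit type as a sensitivity analysis.

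The cost is wording only, since the data are already to be collected. The main model uses 1 of 12 between-unit degrees of freedom; the sensitivity model uses 4, which can cancel the gain at a low ICC or low rho. The text should acknowledge that selecting units for similar baseline composites may weaken that covariate.

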We will perform a nested, multicenter validation study in which we will randomly sample the gloved hands of HCWs entering Contact Precaution-patient rooms in both the intervention and usual care units. Sampling will occur at random and HCWs will not be told in advance that sampling will be performed. A research team member will approach potential participants immediately after gloves are donned and just prior to entering a Contact Precaution-patient room. HCWs will be asked if they have participated in this study previously and those that answer yes will be excluded from participation. Gloved hands of willing HCWs will be sampled via direct imprint of the non-dominant gloved hand onto an agar plate. In addition to sampling of gloved hand, additional data will be collected regarding the date, time and location of the observation, whether the unit was allocated to intervention or usual care, whether the HCW performed HH prior to donning non-sterile gloves, the HCW role (e.g. RN, MD, etc...), when the HCW had started their shift and the time since last performing HH. Each sample will be given a unique number, however, there will be no link to HCW participants and no identifying information will be collected. After sampling, agar plates will be assessed for microbial content including total colony counts and identification of specific pathogenic bacteria including *Staphylococcus aureus*, *Enterococcus*, *Enterobacteriaceae*, *Pseudomonas aeruginosa* and *Acinetobacter baumannii*.

4 Selection and Withdrawal of Participants

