6.2 Sample Size Estimates

Aim 1A:

How many participants (or specimens, or charts) will be used in this study?

UMMC: 6 units Worldwide: 14 units

14 units will be randomized to intervention or usual care. Over the 12-month study period we expect a minimum of 7000 total observations (14 units across the systems x 500 observations). Each system will have a research coordinator perform observations 3 hours per day four days per week. We estimate an average of 5 observations per hour¹⁹ (15 per day and 60 per week) and thus over 2500 observations per year per research coordinator are feasible (we expect to require fewer to achieve desired power). Average HH compliance is consistently at 40-50% and are often lower when glove use is indicated^{1,15}, we believe the compliance with infection prevention practices (i.e. primary outcome, composite compliance with HH AND glove use) in the usual care group will be ~40%. Recent studies have shown compliance with gloves when indicated to be approximately 70-80%¹⁵. Thus for the primary outcome, we expect a difference in compliance with infection prevention practice to be ~ 30%. If we assume 500 observations per area, an alpha level of 0.05, an interclass coefficient of 0.001²² we will require inclusion of 4 patient care areas (2 experimental and

2 usual care) to achieve a power greater than 90% power to detect an effect size of 30% (i.e. the primary outcome). If we vary the interclass coefficient to 0.01, we still have greater than 90% power under the same conditions. Relative to the secondary outcome, in which we will compare compliance with gloving only in both the direct gloving (i.e. experimental group) and the usual care group, we believe it is reasonable to expect that removing the cumbersome and time-consuming requirement of HH prior to glove use may increase compliance with glove use when indicated by approximately 10%. Using the same assumptions as the primary aim with an interclass coefficient of 0.001, we need to recruit and randomize 4 participating units to achieve > 90% power to detect this effect size of 10%. If we use the higher interclass coefficient of 0.01, we need 8 participating units to achieve > 85% power. So in short, we have ample power to see an effect in both primary and secondary outcomes including the sub-populations of adult ICU, dialysis and emergency department.

Aim 1B:

How many participants (or specimens, or charts) will be used in this study?

Local: 866 Worldwide: 2600

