Based on pilot data, we anticipate 5% of HCWs in the usual care group (hand-hygiene plus gloves) and 3.5% in the experimental group (direct gloving) to have > 30 CFUs. We define non-inferiority as a relative risk < 1.15 of having > 30 CFUs, comparing the experimental group to the usual care group. That is, delta equal to 1.15. Under these assumptions, 1280 samples (per group) are sufficient for a one-sided test with alpha=0.025 to have 80% power to detect noninferiority.²³ 1280 samples in both groups will result in a total of 2560 samples for the 12-month study period. Spread across the 14 proposed participating units at the 3 healthcare systems (UMMC and STC will share a Research Associate), this is approximately 850 samples per site and 180 samples per participating unit over the 12-month study period. Thus, each site will need to recruit just over 70 HCWs each month to meet the goal sample size. In the pilot study 230 HCWs were recruited and agreed to participate in a single month.

7 Data Collection, Handling and Storage

All data collected will be stored in a relational database in order to digitize the data for analysis. No PHI will be collected. The database will be stored on a shared drive. Data from University of Iowa and Johns Hopkins Hospital will be sent electronically the investigators at the University of Maryland – data from Aim 1A is aggregate unit level data and not-human subjects data; and data from Aim 1B is completely de-identified.

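### Aim 1B's intention-to-treat comparison is made only among gloved room entries, which the intervention may itself change, and the plan neither adjusts for this nor tests sensitivity to it

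*Combined protocol and SAP*

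**What the plan says.** Section 6.1 (Aim 1B) defines the primary analysis as intention-to-treat: "gloved hands of HCWs sampled in the usual care group will be compared to those in the Intervention group regardless of HH activity". The outcome is more than 30 CFUs on the gloved hand. The arms are compared as proportions, with a relative risk and GEE robust standard errors for clustering. No covariates are named for Aim 1B, although the Aim 1A paragraph of the same section names some. A secondary as-treated analysis compares workers seen to perform hand hygiene (HH) before gloving with those who did not.

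Who can be sampled is set elsewhere. Section 4.2 requires that the "HCW donned non-sterile gloves upon entry to a Contact Precaution-patient room". Section 3 (Aim 1B) says: "A research team member will approach potential participants immediately after gloves are donned and just prior to entering a Contact Precaution-patient room". Section 5.1 describes an earlier contact, "As HCWs approach the room with intent to enter; the investigators will introduce themselves". The two accounts should be reconciled, but on either one section 4.2 still requires gloves to be on. Section 3 also excludes anyone who has taken part before, and records role, shift start and time since last HH with each sample.

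Glove use on entry to Contact Precautions rooms is itself a secondary outcome of Aim 1A (section 3). Section 6.2 gives a current level, "Recent studies have shown compliance with gloves when indicated to be approximately 70-80" per cent, and says that dropping HH before gloving "may increase compliance with glove use when indicated by approximately 10" per cent.

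**The concern.** Intention-to-treat protects a comparison because group membership is fixed by randomisation and nothing afterwards decides who is counted. Here something does. Units are randomised, staff are trained under one policy or the other, and only entries at which gloves are then worn can yield a sample. Ignoring HH activity, as section 6.1 does, deals with non-adherence to HH. It does not deal with whether gloves were worn.

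If direct gloving brings in entries that would otherwise have been ungloved, and these differ in contamination, the arm relative risk mixes two things: the effect of skipping HH, and a change in which entries are sampled. Robust standard errors correct the variance, not the mix. The as-treated analysis also uses gloved hands only, and is not randomised.

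The stakes are real because section 6.1 says that non-inferiority at 1.15 would be enough to change practice. Added entries with more contamination would make non-inferiority harder to show. Added entries with less would make it easier to claim wrongly.

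**Working it through.** **Inputs.** Glove use 70-80%, taken as the usual care level, and a gain of about 10% (6.2, Aim 1A). Anticipated risks from 6.2 (Aim 1B): "we anticipate 5% of HCWs in the usual care group (hand-hygiene plus gloves) and 3.5% in the experimental group (direct gloving"), a relative risk of 0.70. Margin: "We define non-inferiority as a relative risk < 1.15 of having > 30 CFUs". One-sided alpha 0.025, 80% power, 1,280 per group. One further input, k, is an assumption that the documents do not supply: the risk of more than 30 CFUs at added gloved entries, divided by the risk at entries gloved under either policy.

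**The plan's own figure.** On the absolute scale the margin is 0.15 × 5% = 0.75 points, and the distance to it is 0.75 + 1.5 = 2.25 points. Then n = (1.960 + 0.842)² × (0.035 × 0.965 + 0.05 × 0.95) / 0.0225² ≈ 1,261 per group, close to 1,280; power at 1,280 is 80.6%. A Wald test on the log relative risk needs 1,483, and has 74.0% power at 1,280. That gap is a separate matter, but it is why two baselines appear below.

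**Share of added entries.** With glove use g0 under usual care and g1 under intervention, and nobody gloving less under the intervention, s = (g1 − g0)/g1.
- 70% to 80%: 10/80 = 12.5%
- 80% to 90%: 10/90 = 11.1%
- a relative gain of 10%, for example 70% to 77%: 7/77 = 9.1%

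**Effect on the relative risk.** Observed RR = true RR × (1 − s + s·k), where the true RR refers to entries gloved under either policy.

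| k | s = 12.5% | s = 11.1% | s = 9.1% |
|---|---|---|---|
| 0.5 | 0.94 | 0.94 | 0.95 |
| 1.5 | 1.06 | 1.06 | 1.05 |
| 2 | 1.125 | 1.11 | 1.09 |

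**Consequences at s = 12.5%, 1,280 per group, 5% control risk, no clustering.**
- True RR 0.70: the chance of showing non-inferiority goes from 74.0% to 64.3% (k = 1.5) or 53.8% (k = 2) on the log scale, and from 80.6% to 71.2% or 60.3% on the absolute scale.
- True RR 1.15, k = 0.5: the observed RR is 1.15 × 0.9375 = 1.08, and the false non-inferiority rate goes from 2.5% to 5.7% (log scale).

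**How large k must be to reach the margin by selection alone.** k = 1 + (1.15/true RR − 1)/s. From a true RR of 1.0: 1 + 0.15/0.125 = 2.2, then 2.35 and 2.65 for the two smaller shares. From a true RR of 0.70: 1 + 0.643/0.125 = 6.1, then 6.8 and 8.1.

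**Information available for adjustment.** Expected events are 1,280 × 0.05 + 1,280 × 0.035 = 64 + 44.8, about 109, in 14 units. Section 3 gives four adult ICUs, four emergency-type units, three paediatric wards and three dialysis units. A stratum of three cannot split evenly, so unit type will not be balanced between arms.

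**The case against.** The strongest reply is that contamination of gloves can be measured only on gloved hands. Contamination of gloves as worn under each policy is a legitimate effectiveness question, and section 6.1 openly says that the comparison is of sampled gloved hands. This stands, and it is why the remedy should not ask for a different population. It does not rescue the label, or explain why nothing is planned for a differing mix.

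A reader might infer that the two arms sample different workers, and that 11-12.5% of intervention samples come from people who would never be sampled under usual care. The documents do not support that. The glove rates in 6.2 are per observed entry, while section 3 samples each worker once. Someone who gloves at 70% of entries can still be sampled at one of them. If the same workers simply glove more often, the mix of workers barely changes and only the mix of entries may shift.

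A reader might also infer that better glove use will be scored as contamination. That needs k above 1, which no section shows. Sections 1.1 and 1.2 report no difference in glove colony counts with or without HH among 230 workers, and 6.2 anticipates fewer high counts with direct gloving. This does not establish k = 1, but it makes k = 2 through dirtier hands harder to motivate.

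Finally, the 10% is a possibility stated to power a secondary outcome, not a firm forecast, and about 109 events in 14 units limit how much adjustment a model can carry. Both points stand and shape the fix.

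**Conclusion.** The concern holds in a limited form. The primary Aim 1B comparison is conditional on a behaviour that arises after randomisation and that the intervention is meant to alter. Calling it intention-to-treat therefore claims more than the design delivers, and the plan has no adjustment or sensitivity analysis for it.

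The direction of any bias is unknown. For k between 0.5 and 1.5 the relative risk moves by about 6% either way; at k = 2 it moves by up to 12.5%. These are upper-range illustrations. They assume that the whole gain consists of newly gloved entries which feed through to samples in proportion, that nobody gloves less under the intervention, and that samples are independent. If the planned relative risk of 0.70 is true, selection alone will not plausibly carry the result past the margin, since k would have to be about 6 or more; the likely cost is power. If there is no true difference, k of about 2.2 to 2.65 would put the observed relative risk at the margin. If glove use turns out equal between arms, this route largely closes, unless the kinds of entry that are gloved still differ.

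**What to change.** In section 6.1, Aim 1B:

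1. Describe the primary analysis as a comparison of randomised arms among gloved entries, regardless of HH activity.
2. Fit the primary GEE with a log link and include unit type, the randomisation stratum. Add role and hours since shift start in the same model or, if it is unstable with about 109 events in 14 units, in a pre-specified supporting model. Leave out time since last HH, because the gloving policy may affect it.
3. Report Aim 1A glove use by arm beside the Aim 1B result. Add a tipping-point analysis that takes s from those rates, divides the relative risk and its upper confidence limit by (1 − s + s·k) for k from 0.5 to 2, and gives the k, if any, at which the non-inferiority conclusion changes. State its assumptions: the share is at entry level although each worker is sampled once, and nobody gloves less under the intervention.

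The cost is SAP wording and a short extra analysis. Unit, role and shift start are already recorded, and glove use by arm is already an Aim 1A outcome. The one downside is possible model instability, which the supporting-model option covers. Adjustment cannot remove unmeasured differences between entries, so item 3 is needed as well as item 2.
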